7.3 Random Assignment

Upon enrolling in the study, each participant will be assigned at random to one of six possible sequences of product use. Two randomization schedules will be used to ensure balanced sequence assignment among circumcised and uncircumcised men. Specifically, two circumcised men and two uncircumcised men will be assigned to each sequence.

The SDMC will provide the study site with two series of numbered, sealed, opaque envelopes containing the random assignments for circumcised and uncircumcised participants. Site staff will assign the envelopes to participants sequentially, in the order in which they are enrolled in the study. The envelopes and their contents will be maintained in participants' study records.

7.4 Blinding

Throughout the period of study implementation and data analysis, neither study staff nor participants will be informed of the identity of product applied each week by individual study participants. Study staff and participants will be unblinded after all study visits and data analyses are completed.

Exceptions may be considered by the Protocol Clarifications Team (see Section 10.1) in situations where product information may be needed to protect the safety of the participant. In emergency situations, if a participant experiences an SAE that, in the opinion of the Investigator requires immediate unblinding, the study site pharmacist may disclose the treatment assignment to the Investigator without obtaining prior concurrence of the Protocol Clarifications Team.

7.5 Data Monitoring

Close collaboration between the Investigator, NIAID Medical Officer, Protocol Coordinator, and SDMC Biostatistician will be necessary to evaluate study progress and respond to occurrences of toxicity in a timely manner. Rates of accrual, adherence, follow-up, and AE incidence will be monitored closely by the study team on a regular basis.

The Investigator will be responsible for continuous close monitoring of all AEs that occur among study participants, and for alerting the rest of the study team if unexpected concerns arise. All concerns then will be addressed according to DAIDS and HPTN standard operating procedures. In particular, for this study, accrual will be suspended if two or more grade 3 or higher AEs (as defined by the DAIDS Standard Toxicity Tables) judged possibly, probably, or definitely related to product use are observed across at least two study participants (i.e., the study will not be stopped if two more related grade 3 AEs are observed in a single participant). The study team then will review all pertinent safety data and determine whether to continue accrual and product use. A decision to stop the

trial may be made by the study team at this time, or at any such time that the team agrees that an unacceptable type and/or frequency of AEs has been observed.

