Particularly in light of the most recent findings with respect to the effects of nonoxynol-9 products, increasing attention has been given to developing non-detergent topical microbicides to prevent HIV infection. Two such products are BufferGel, developed by Reprotect, LLC, and PRO 2000/5 Gel (P), developed by Procept, Inc. and acquired recently by Interneuron Pharmaceuticals, Inc. BufferGel is designed to protect against HIV infection by maintaining the normally acidic pH of the vagina in the presence of ejaculate. PRO 2000/5 Gel (P) is designed to protect against HIV infection by inhibiting viral entry into susceptible cells.

BufferGel and PRO 2000/5 Gel (P) currently are not approved by the US Food and Drug Administration (FDA) for any use. However, both products have undergone extensive pre-clinical testing, both have been shown to inhibit/inactivate HIV in vitro, and both are compatible with condoms. Both products also have undergone clinical testing in Phase I trials among healthy HIV-uninfected sexually abstinent and sexually active women. PRO 2000/5 Gel (P) also has been tested among HIV-infected women. In these studies, the products were shown to be safe and acceptable for vaginal use [10-13].

Phase I trials also have been conducted to assess the safety of BufferGel and PRO 2000/5 Gel (P) on the penile epithelium and urethral mucosa. In one trial, HIV-uninfected men applied either PRO 2000/5 Gel (P) (n=24) or a gel containing the inactive ingredients of PRO 2000/5 Gel (P) (n=12) to the penis for seven consecutive days. About one in three users of the active gel and one in four users of the inactive gel reported mild symptoms of genital itching, tingling, irritation, dryness, discoloration, or flaking of the dried gel. In a similar trial comparing BufferGel and K-Y Jelly (a marketed sexual lubricant), about one in eight users of BufferGel and one in six users of K-Y Jelly reported similar symptoms.

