3.4 Participant Withdrawal

Once a participant has enrolled in the study, the study site will make every reasonable effort to retain him for the entire five-week study period. Given the small study sample size, and the importance of ascertaining all safety outcomes among study participants, 100 percent retention of enrolled participants is targeted. Study site staff are responsible for developing and implementing local standard operating procedures to achieve complete follow-up.

However, participants may withdraw from the study for any reason at any time. The Investigator also may withdraw participants from the study in order to protect their safety (e.g., due to intolerance of the study products or development or exacerbation of a concomitant medical condition) and/or if they are unwilling or unable to comply with required study procedures. In particular, participants who experience vesiculation, bullous reaction, or ulceration, or are diagnosed with a confirmed STD, will be followed until the condition resolves and then will be withdrawn from the study (see Appendix III). Participants who voluntarily withdraw from the study, are withdrawn by the Investigator, or are not adherent to the study product application regimen, as defined in Section 4.5, will be replaced.

Participants also may be withdrawn if the study sponsor or regulatory authorities terminate the study prior to its planned end date.

Every reasonable effort will be made to complete a final evaluation of participants who terminate from the study prior to Day 35, and study staff will record the reason(s) for all withdrawals from the study in participants' study records.

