8.8 Study Discontinuation

As noted in Section 7.5, accrual into this study will be suspended if two or more grade 3 or higher AEs (as defined by the DAIDS Standard Toxicity Tables) judged possibly, probably, or definitely related to product use are observed across at least two study participants. The study team then will review all pertinent data and determine whether to continue accrual and product use. A decision to stop the trial may be made by the study team at this time, or at any such time that the team agrees that an unacceptable type and/or frequency of AEs has been observed.

The study also may be discontinued at any time by NIAID, the HPTN, the manufacturers of the study products, and/or the FDA or other regulatory authorities.

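### The study-level safety trigger makes only the suspension of accrual automatic; men already using the gels may be paused but need not be until the review decides

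*Protocol*

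**What the plan says.** Protocol section 7.5 sets a trigger specific to this study: "accrual will be suspended if two or more grade 3 or higher AEs" judged at least possibly related to product occur in two or more different men. The next step is a review: "The study team then will review all pertinent safety data and determine whether to continue accrual and product use". Section 8.8 repeats the rule ("accrual into this study will be suspended if two or more grade 3 or higher AEs") with the same order of events: suspend accrual, review, then decide on accrual and product use.

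Several provisions allow wider action:

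- The team may stop the trial at the review or "at any such time that the team agrees that an unacceptable type and/or frequency of AEs has been observed" (section 7.5).
- "The study also may be discontinued at any time by NIAID, the HPTN, the manufacturers of the study products", as may the FDA or other regulators (section 8.8).
- "The Investigator also may withdraw participants from the study in order to protect their safety" (section 3.4).
- On concerns raised by the investigator, section 7.5 states: "All concerns then will be addressed according to DAIDS and HPTN standard operating procedures". Those procedures are not reproduced in the protocol.

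Product discontinuation in section 4.6, section 6 and Appendix III concerns the man who has the sign or symptom. Re-screening on days 14 and 28 (section 5.5) looks at each man's own condition.

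**The concern.** Once two men have had related grade 3+ events, the people at immediate risk are those applying a gel that night, with staff and participants blinded to which gel it is. The only step that must happen at that moment concerns men who have not yet enrolled. Whether current users are paused before the review ends depends on someone choosing to use a discretionary power.

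The mismatch grows late in the study. Accrual is planned over two to three months and each man is exposed over 35 days, so a substantial share of dosing follows the last enrolment. By then the automatic step has only replacement enrolments to hold back, although the review itself still takes place.

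**Working it through.** **Reading the rule.** The table sets out each provision that could stop a man's dosing.

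| Provision | Acts on | Mandatory? |
|---|---|---|
| 7.5 and 8.8, trigger | accrual | yes |
| 7.5 and 8.8, review | accrual and product use | the review must take place; its outcome is open |
| 7.5, team stop at any time | whole trial | no |
| 8.8, sponsor, network, manufacturers, regulators | whole trial | no |
| 3.4, investigator withdrawal for safety | individual man | no |
| 4.6, 6, Appendix III | the affected man | yes for specified signs |
| 5.5, re-screening | each man's own findings | yes |

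None of these requires unaffected enrolled men to hold product while the review is pending.

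**Chance that the trigger is met.** The protocol gives no rate of related grade 3+ AEs, so the per-man rate p is an assumption. With 24 men, P(2 or more) = 1 − (1−p)^24 − 24p(1−p)^23. At p = 1% this is 1 − 0.7857 − 0.1905 = 0.024. At 5% it is 1 − 0.2920 − 0.3688 = 0.339. At 10% and 20% it is 0.708 and 0.967. Section 7.2 tabulates .02, .34, .71 and .97 for these rates, so its figures are reproduced. At 2%, which it does not tabulate, the result is 0.083.

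**Exposure after the last enrolment.** Section 7.2 expects 9-12 men per month and 24 within three months. With even entry, the gap g is 30.4/9 = 3.38, 30.4/12 = 2.53 or 91.25/24 = 3.80 days, so the 24th man enters on day 23g = 77.7, 58.3 or 87.4. Product is used on days 0-7, 14-21 and 28-35 from entry. That is 21 days per man and 24 × 21 = 504 man-days. Adding the part of each product week that falls after day 23g gives:

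- 9 per month: 119.5/504 = 23.7%
- 12 per month: 155.9/504 = 30.9%
- three months: 107.3/504 = 21.3%

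**What happens at the trigger.** This was simulated. Each man has one qualifying event with probability p at a uniform time over his product days, and the trigger is the second man's event. Men with an event stop dosing, washouts are the minimum, and there are no replacements. The chance that the trigger is first met after the 24th enrolment is:

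| p | 9/month | 12/month | three months |
|---|---|---|---|
| 1% | 0.010 | 0.012 | 0.009 |
| 2% | 0.031 | 0.040 | 0.028 |
| 5% | 0.107 | 0.139 | 0.096 |
| 10% | 0.151 | 0.206 | 0.132 |
| 20% | 0.064 | 0.100 | 0.053 |

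Means, with ranges over all five values of p:

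| Quantity | 9/month | 12/month | three months |
|---|---|---|---|
| Trigger met: other men on product | 4.1-4.4 | 5.4-5.8 | 3.7-3.9 |
| Trigger met: doses in next 3 days | 11.8-12.6 | 15.3-16.5 | 10.5-11.1 |
| Trigger met: doses in next 7 days | 26.3-27.9 | 33.7-36.3 | 23.5-24.8 |
| Trigger met: days already used in the current product weeks | 14.4-15.2 | 19.0-20.1 | 12.9-13.4 |
| First met after last entry: other men on product | 3.0-3.4 | 4.1-4.9 | 2.6-2.9 |
| First met after last entry: planned doses still ahead | 50-61 | 65-84 | 44-53 |

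The dose counts cover unaffected men on product at the trigger and enrolled men who start their day-14 or day-28 period during the review. The review lengths of 3 and 7 days are assumptions; the protocol gives none.

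**The case against.** The strongest reply is that nothing here is contradictory. Sections 7.5 and 8.8 agree, the review expressly covers product use, and several parties can halt dosing at any time. Section 7.5 places its trigger within DAIDS and HPTN procedures that may themselves pause dosing. Its parenthesis about two events in a single man speaks of the study being stopped, so the authors may have meant a wider halt. Enrolled men also have close monitoring, immediate AE reporting, wash-off instructions and Appendix III, which stops the current product at definite erythema. All of this stands as mitigation. It does not supply a required pause for unaffected men. If a wider halt was meant, the operative wording should say so.

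The second reply is that doses are not harms. In the same model, the expected number of further qualifying events in already enrolled men during a 3-day review, given the trigger, is about 0.01-0.02 at p = 2%, 0.03-0.04 at 5% and 0.06-0.08 at 10%. For a 7-day review at 5% it is 0.06-0.09. Only at 20% is it material: 0.12-0.17 in 3 days and 0.26-0.37 in 7 days. If use resumes and the remaining nights are completed, doses are postponed and not avoided, so the gain comes when the review ends in a stop. This is a fair limit on the size of the point and the reason to rank it low.

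**Conclusion.** The point holds as a design choice worth changing. The one mandatory action at the study-level trigger does not reach the men then exposed, and the protocol leaves continued dosing as the default until the review decides.

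The practical size is modest and conditional. The trigger may well never be met, since users in one earlier trial in men "reported mild symptoms of genital itching, tingling, irritation, dryness, discoloration, or flaking of the dried gel" and section 1.1 describes similar symptoms in the other. The magnitudes rest on assumed event rates and review lengths and on the simplifications listed above; the reading of the rule rests on none of them. The claim is limited to the protocol text, because the DAIDS and HPTN procedures might add a pause.

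**What to change.** In sections 7.5 and 8.8, replace the suspension of accrual alone with: *accrual and all further dispensing and use of study products will be suspended until the study team has completed its review and decided; this applies until the last participant's final visit.*

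In section 4.5 add: *Nights missed because of a study-level suspension do not make a participant non-adherent; if use resumes, the study team decides, after re-screening, whether the man completes the remaining nights or moves to the next product after washout, and he still contributes once per product to event rates.* Without this, a pause of more than two nights would fall outside the adherence definition and lead to withdrawal and replacement, because the existing exception covers only a man's own AE.

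The change is wording in three sections and has no effect unless the trigger is met. The new prescription needed for each product period (section 4.1.3) already gives a means to hold dispensing. If the trigger is met, visits are delayed by the length of the review and about 4-6 men have an interrupted product week. A man moved on has fewer than seven nights on that product. Because the trigger counts possibly related events and is not product-specific, two events on placebo would pause all three gels.

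Interrupted weeks should not be repeated in full. Completing the remaining nights adds no doses, whereas repeating whole weeks would re-apply about 13-20, which offsets the 11-17 held back during a 3-day review.

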7.6 Data Analysis

Primary data analyses will tabulate the number of observed primary endpoints — listed in Section 7.1.1 — by product and circumcision status.

All participants who enroll in the study will be included in each tabulation. Individual participants will contribute once to the calculation of event rates for each product. Additional safety analyses will tabulate the number and type of AEs experienced during use of each product, overall and by severity and relationship to product. The temporal relationship of product application and AE onset, and the duration of symptoms, also will be evaluated.

Due to the modest study sample size, statistical comparisons across products will not be performed. However, analyses will be performed to assess the number and proportion of participants with subjective or objective findings across products, to determine whether individual participants had similar symptoms and/or exam findings across products.

Additional data analyses will tabulate the number and type of positive and negative product attributes reported by study participants on the Acceptability Assessment completed after use of each product. Also tabulated will be the number and percent of participants who report willingness to use each product for sexual intercourse on the Acceptability Assessment. As above, statistical analyses across products will not be performed, however data will be evaluated to determine whether individual participants' had similar perceptions across products.

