2 STUDY OBJECTIVES AND DESIGN

2.1 Primary Objective

To assess the toxicity of BufferGel and PRO 2000/5 Gel (P) on the penile epithelium and urethral mucosa of HIV-infected men.

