7 STATISTICAL CONSIDERATIONS

7.1 General Design

This is a Phase I, randomized, blinded, crossover study with one week of participant exposure to each of two investigational products — BufferGel and PRO 2000/5 Gel (P) — and a placebo control gel. Each week of exposure will be separated by a minimum one-week washout period. Participants will be assigned at random to one of six possible sequences of product use, balanced within circumcised and uncircumcised participants. Product safety and acceptability will be assessed after application of each product once nightly for a period of seven consecutive nights.

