7.2 Sample Size and Accrual

A minimum of 24 "adherent" (as defined in Section 4.5) HIV-infected men — 12 circumcised and 12 uncircumcised — will be included in the study. Based on preliminary estimates, it is expected that 9-12 participants will be enrolled per month, and that 24 participants will be accrued within three months. Additional participants may be included in the study as needed to replace non-adherent participants, as described in Section 4.5.

The table below presents the probability of observing either zero or two or more safety outcomes among groups of 12 (circumcised or uncircumcised) or 24 (circumcised and uncircumcised) participants for various "true" event rates.

	P(0 events observed)		P(2+ events observed)	
Event Rate	n=12	n=24	N=12	n=24
1%	.89	.79	<.01	.02
5%	.54	.29	.12	.34
10%	.28	.08	.34	.71
20%	.07	.005	.73	.97
30%	.01	<.001	.91	>.99
40%	.002	<.001	.98	>.99
50%	<.001	<.001	>.99	>.99

Based on the above, if any safety outcome occurs at a rate of less than five percent, then the probability of observing at least two such events is 12 percent among 12 participants (e.g., the subset of uncircumcised men) and 34 percent among 24 participants. Alternatively, 12 participants provide 91 percent power to exclude event rates of 30 percent or more, and 24 participants provide 97 percent power to exclude event rates of 20 percent or more.

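### Section 7.2 presents the probability of seeing two or more events as power to exclude a rate, and Section 7.6 sets no bound that would deliver that exclusion

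*Protocol*

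**What the plan says.** Section 7.2 sets the size at no fewer than 24 adherent men, 12 circumcised and 12 uncircumcised. Its table gives "the probability of observing either zero or two or more safety outcomes among groups of 12" or 24, for true rates from 1% to 50%. From the table the text concludes that "12 participants provide 91 percent power to exclude event rates of 30 percent or more" and that "24 participants provide 97 percent power to exclude event rates of 20 percent or more". It gives no confidence level and no rule for when a rate counts as excluded.

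Section 7.1 describes the design: "This is a Phase I, randomized, blinded, crossover study with one week of participant exposure to each of two investigational products", plus a placebo gel, which Section 4.3.3 identifies as K-Y Jelly. The objective in Section 2.1 is "To assess the toxicity of BufferGel and PRO 2000/5 Gel (P) on the penile epithelium and urethral mucosa of HIV-infected men".

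Section 7.6 says: "Primary data analyses will tabulate the number of observed primary endpoints", split by product and circumcision status. Event rates are calculated per product, with each man counted once per product. It then says: "Due to the modest study sample size, statistical comparisons across products will not be performed". In place of comparisons it plans a descriptive look at whether individual men had similar findings on the different gels.

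**The concern.** Excluding a true rate means that the data, through a confidence bound or a stated rule, show the rate to be lower. The figures in Section 7.2 answer a different question: if the rate really were 30% or 20%, how likely is it that at least two events appear? A reader who takes 91% or 97% as the chance that the trial will rule out such rates is misled, because that chance depends on how low the true rate is. Section 7.6 does not repair this, since nothing in it turns an observed count into an exclusion.

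The wording of the bar on comparisons adds a second difficulty. It is broad enough to cover estimates as well as tests. An analysis plan that added an active-minus-placebo estimate would arguably conflict with the protocol. The stated reason, small size, is an argument against testing; it does not argue against showing the paired data with their uncertainty.

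**Working it through.** **Inputs.** n = 12 and n = 24, rates of 30% and 20%, and the stated 91% and 97%, all from Section 7.2. No confidence level is given, so one-sided and two-sided 95% are both shown as assumptions.

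**Step 1. Reproduce the plan's figures.** P(2 or more) = 1 − (1−p)^n − n·p·(1−p)^(n−1).

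- n = 12, p = 0.30: 1 − 0.0138 − 0.0712 = 0.915 (stated 91%).
- n = 24, p = 0.20: 1 − 0.0047 − 0.0283 = 0.967 (stated 97%).

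The other table cells also reproduce. The arithmetic is right; the label is wrong.

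**Step 2. Error of the implied rule.** If two or more events means not excluded, then at most one event means excluded. The chance of wrongly excluding a rate that is truly at the limit is the complement:

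- 12 men, 30%: 0.0138 + 0.0712 = 0.085.
- 24 men, 20%: 0.0047 + 0.0283 = 0.033.

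**Step 3. What an observed count excludes.** The exact (Clopper-Pearson) upper limit is the p that solves P(X ≤ x | n, p) = α, with α = 0.05 one-sided or 0.025 two-sided.

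| Events | One-sided 95% | Two-sided 95% |
|---|---|---|
| 0 of 12 | 22.1% | 26.5% |
| 1 of 12 | 33.9% | 38.5% |
| 0 of 24 | 11.7% | 14.2% |
| 1 of 24 | 18.3% | 21.1% |

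In 12 men only a zero count excludes 30% at either level. In 24 men one event excludes 20% one-sided but not two-sided.

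**Step 4. Chance of meeting the implied rule (at most one event).**

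| True rate | 12 men | 24 men |
|---|---|---|
| 5% | 88% | 66% |
| 10% | 66% | 29% |

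These are the figures that would deserve to be called power to exclude under that rule. For 24 men they lie well below 97%. In 12 men, if a zero count is required so that 30% is excluded at the 5% level, the chance is 0.95^12 = 54% at a true rate of 5% and 0.90^12 = 28% at 10%.

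**Step 5. Is the bar on testing reasonable?** Exact McNemar power with 24 pairs, two-sided 5%, within-man dependence varied from none to maximal, using the prior symptom rates in Section 1.1:

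- 1/3 against 1/4: 1% to 5%.
- 1/8 against 1/6: at most 2%.
- 1/3 against 1/6, which pairs arms from two different trials: 16% to 20%.

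At least six discordant men, all in one direction, are needed for p < 0.05 (2 × 0.5^6 = 0.031; five give 0.0625). Dropping tests is sound.

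**Step 6. What a paired estimate would show.** For a hypothetical 8/24 against 4/24, the difference is 17 points. The 95% score interval is −7 to 39 points with 6 against 2 discordant men, and 0.6 to 36 points with 4 against 0. In the second case the exact McNemar p is 2 × 0.5^4 = 0.125 although the interval excludes zero. Such intervals therefore need an explicit estimation-only label.

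**The case against.** The strongest reply is that this is loose wording in a small Phase I study. Section 7.2's table is correct and itself shows that a zero count is compatible with a double-digit rate: P(0 events) is .08 at 10% in 24 men. Any reader can derive exact limits from the planned counts. Interval methods are commonly left to an analysis plan, which is not shown. Section 2.1 names no contrast with placebo, and Section 1.2 makes experience in women the benchmark for studies in men.

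Much of this stands. A missing interval alone would not be a finding, and a decision not to test is well founded. A reader might infer more: that the plan yields bare counts, ignores the within-man structure, and so can neither exclude a rate nor use its placebo. The protocol does not support that. Section 7.6 plans rates, proportions and a descriptive look across products within men, K-Y Jelly is tabulated beside both active gels, and limits can be computed from the counts.

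A paired table also carries a real hazard. Sections 3.4 and 4.6 withdraw men with vesiculation, bullous reaction or ulceration once the condition resolves. A table of complete pairs would lose those withdrawn before using both gels, and with them some of the most serious findings.

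What the reply does not answer is that Section 7.2 states its own justification wrongly, and that the bar in Section 7.6 is protocol text, not a detail left open for an analysis plan.

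**Conclusion.** The concern holds in a limited form. The 91% and 97% are correct probabilities of two or more events but are mislabelled as power to exclude. The implied rule fails at the conventional 5% level for 12 men at 30% (error 8.5%). It passes for 24 men at 20% only one-sided (error 3.3%; upper limit 18.3% one-sided, 21.1% two-sided). Section 7.6 gives no bound linked to the claim, and its bar on comparisons is wider than its reason supports.

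This rests on two assumptions: that the rule implied by the table is at most one event, and a 95% confidence level, since the protocol states neither. The prior-trial rates serve only as illustration; the symptoms listed in Section 1.1 match the primary endpoints only in part.

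**What to change.** 1. **Section 7.2.** Relabel the 91% and 97% as the probability of observing at least two events at the stated rate. Alternatively, state the exclusion rule and confidence level with its true error.
2. **Section 7.6, rates.** Report each primary-endpoint rate per product, overall and by circumcision status, with an exact 95% interval.
3. **Section 7.6, comparisons.** Replace the bar on statistical comparisons with a statement that no hypothesis tests across products will be performed.
4. **Section 7.6, paired data.** For each active gel against K-Y Jelly, show a descriptive within-man table with discordant counts, optionally with a score interval labelled as estimation only. List separately the men withdrawn before completing both products, so that their events are not dropped.

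The cost is some wording and a few table columns from data already collected, with no added participants or visits. The downside is that the intervals will be wide. Four primary endpoints and two active gels also give eight unadjusted contrasts overall, which must not be read as tests.
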